10.6 Interim analysis

No interim analysis will be performed.

10.7 Deviation from the original statistical plan

Should any deviations from the statistical plan be necessary, these shall be detailed in an amendment to the study protocol and declared in any publications. Unplanned interim analysis, not described in the original study protocol shall be registered in an amendment to the protocol.

10.8 Handling of missing data and drop-outs

Missing postoperative VAS/NRS scores, required for primary and secondary endpoints, will be handled as interpolation values, calculating an average score between last recorded scores before and after the missing value. Missing data for secondary endpoint PONV or time to first defecation will be handled as no occurrence of PONV (PONV 0) or no defecation yet. In case of drop-out, data collected till patients drop out will be neglected and not taken into account of statistical consideration of the study.

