5. STUDY OUTCOMES

5.1 Primary outcome

Any development of VAS/NRS score > 3 , in hourly measurements within the first four hours after completion of bariatric surgery.

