Study intervention: Patients in the “lidocaine group” will receive 1.5 mg/kg lean body mass of lidocaine 1% bolus intravenously after induction of general anesthesia (as soon

as general anesthesia's steady state is accomplished), followed by a continuous infusion of lidocaine 1% with 1.5 mg/kg lean body mass/h during surgery and continued for four hours after completion of surgery or until the discharge from the PACU, whatever comes first. Patients in "placebo group" will receive 0.15 ml/kg lean body mass of saline 0.9% bolus I.V. after induction of general anesthesia (as soon as general anesthesia's steady state is accomplished), followed by continuous infusion of NaCl 0.9% I.V. with 0.15 ml/kg lean body mass/h during surgery and continued for four hours after completion of surgery or until the discharge from the PACU, whatever comes first. Maintenance of general anesthesia and optional application of additional opiates for pain treatment (fentanyl 0.1 - 0.2 mg as an intravenous bolus) during surgery is under discretion of the attending anesthesiologist and is related to the practice of standardized pain management and will be equal in both groups. Similarly, postoperative treatment in the PACU and further on the surgical ward, are under discretion of the clinically responsible physicians, relating to current practice of standardized pain management at the Kantonsspital St. Gallen (Schmerzkarte KSSG).

A detailed graphical version of study sequences is provided in german as follows:

Periode	Ort	Intervention	Details
Anmeldung	Studien- koordination	Screening	Ein- / Ausschlusskriterien evaluieren
		erfüllt	
PAS Termin	PAS	Informed consent	Aufklärung und Einwilligung durch Patienten
		erfüllt	
PAS Termin	PAS	Randomisierung	Zuteilung zur Gruppe Lidocain oder Placebo
OP Datum	OPS 03	Intervention COALAS	- IMP Bolus ab AN steady state - anschliessend Beginn IMP Perfusor - Datenerfassung ACPDMS (Medis, Vitalparameter) - AE, SAE, ADR erfassen
		Transfer	
POD 0	PACU	VAS Monitoring VAS Evaluationsbogen	- IMP Perfusor bis 4 Std. ab "OP-Ende" od. Transfer auf Abteilung - VAS 1.,2.,3.,4. Std. - Datenerfassung ACPDMS (Medis, Vitalparameter) - Prim./Sek. Variablen im CRF erfassen - AE, SAE, ADR erfassen
		Transfer	
POD 0	ABTEILUNG	VAS Monitoring 2pm, 10pm Studiensite 10am, 2pm	- Erinnerung des Pat. durch Pflege- Studienpersonal - Prim./Sek. Variablen im CRF erfassen - AE, SAE, ADR erfassen

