POD 1	ABTEILUNG	VAS Monitoring 6am, 2pm, 10pm Studiensite 10am, 2pm	- Erinnerung des Pat. durch Pflege- Studienpersonal - Prim./Sek. Variablen im CRF erfassen - AE, SAE, ADR erfassen
POD 2	ABTEILUNG	VAS Monitoring 6am, 2pm Studiensite 10am, 2pm (Safety follow-up)	- Erinnerung des Pat. durch Pflege- Studienpersonal - Prim./Sek. Variablen im CRF erfassen - AE, SAE, ADR erfassen
POD X	Studien- koordination	Safety follow-up	- telefonisch / ambulant - AE, SAE, ADR erfassen

table 2: study sequence describing process and daily course, POD X will be postoperative day seven or day of patients discharge

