9.2 Assessments of outcomes

Assessment of Pain

Pain will be assessed by the visual analogue scale (VAS) or the numeric rating scale (NRS), respectively, 0 indicating no pain and 10 maximal possible pain sensation. VAS/NRS scoring systems are validated and frequently used methods to evaluate variations in pain intensity. The VAS/NRS score will be recorded by trained nurse practitioners in the PACU, respectively on the surgical ward, once per hour during the first four hours after completion of surgery. Analysis of the primary outcome (any development of

VAS/NRS score > 3, in hourly measurements within the first four hours after completion of surgery) will be dichotomized accordingly. Thereafter, VAS/NRS score will be assessed by a patient questionnaire for self-evaluation and in addition by trained nurse practitioners during their daily round (10am and 2pm respectively +/- 30 minutes) during the first 48 hours after completion of surgery. Missing postoperative VAS/NRS scores, required for primary and secondary endpoints, will be handled as interpolation values, calculating an average score between last recorded scores before and after the missing value.

Secondary endpoints

- Average maximal pain intensity during first four hours and during 48 hours
- total amount of opiates as documented in the electronic anesthesia records during surgery and on PACU
- total amount of opiates applied on surgical ward, recorded in the charts. Values will be categorized in total amount in mg, average amount in mg/h and indexed amount in mg/kg bodyweight/h
- any event of postoperative nausea and vomiting (subdivided by event of no nausea (PONV = 0), event of nausea without vomiting (PONV = 1) and event of nausea with vomiting (PONV = 2)) during first 48 hours after completion of surgery
- time to first defecation after completion of surgery (quantified in hours)
- total time spent in hospital after completion of surgery (quantified in days)

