9.4 Procedures at each visit

Each patient will be visited after surgical treatment and transfer to PACU/ICU by a study nurse or the Study Investigator. The VAS/NRS score (registration of any development of VAS/NRS score > 3) will be assessed by trained nurse practitioners in the PACU/ICU in hourly measurements during the first four hours after completion of surgery, respectively until discharge to the surgical ward. Thereafter, VAS/NRS score will be assessed by a patient questionnaire for self-evaluation and in addition by trained nurse practitioners during their daily round (10am and 2pm respectively ± 30 minutes) during the first four hours and during 48 hours after completion of surgery. VAS/NRS scores and vital parameters will be recorded. Incidental questions about upcoming study process will be answered. Infusion of the investigational product will be stopped four hours after the end of surgery (or before the transfer of the patient from the PACU to the surgical ward, whichever occurs first). Pain evaluation will take place every eight hours by recording the maximum VAS/NRS score experienced within this period. Recording of VAS/NRS scores will be stopped at 2pm respectively ± 30 minutes on second postoperative day. Completion of study investigation will be finalized by collecting the study documents at study nurses final visit on second postoperative day at 2pm respectively ± 30 minutes.

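### Filling a missing hourly pain score with the mean of its neighbours does not suit an any-hourly-score-above-3 primary endpoint

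*Combined protocol and SAP*

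**What the plan says.** Section 5.1 defines the primary outcome as any VAS/NRS score above 3, "in hourly measurements within the first four hours after completion of bariatric surgery". It is binary, and one high score is enough.

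The rule for gaps appears twice. Section 9.2 says: "Missing postoperative VAS/NRS scores, required for primary and secondary endpoints, will be handled as interpolation values". Section 10.8 repeats it: missing scores "will be handled as interpolation values, calculating an average score between last recorded scores before and after the missing value". Neither section makes an exception for the first or last hour, and no sensitivity analysis for missing scores is given.

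On where the hourly scores are taken:

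- Section 9.2 has them recorded "in the PACU, respectively on the surgical ward, once per hour during the first four hours after completion of surgery".
- Section 9.4 has them recorded in the PACU/ICU "in hourly measurements during the first four hours after completion of surgery, respectively until discharge to the surgical ward". It then turns to the patient questionnaire and the nurse rounds.
- Section 5.2 has hourly scores in the PACU and eight-hourly scores on the ward, but it defines a secondary outcome.
- The study sequence table in Section 8.1 lists hours 1 to 4 in its PACU row only.

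The ward self-rating is not a point score. Section 9.4: "Pain evaluation will take place every eight hours by recording the maximum VAS/NRS score experienced within this period". The table in Section 8.1 fixes its clock times: "VAS Monitoring 2pm, 10pm" on the day of surgery and "VAS Monitoring 6am, 2pm, 10pm" on the next day.

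**The concern.** An endpoint that asks whether any score crossed a threshold depends on peaks, and averaging neighbours removes peaks. The rule also assumes a usable score on both sides of the gap. That fails at hour 1 and is doubtful at hour 4.

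At stake is the classification of the only primary endpoint in patients who have a missing hourly score and no recorded score above 3. In these patients the rule can lose a real event. At hour 4 it can also create an event from pain felt after the four-hour window. Hour 1 is left for the analyst to settle later.

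The differing wording in Sections 9.2 and 9.4 matters because it affects how often hours 3 and 4 will be missing. Section 8.2 gives four hours in the PACU as an average, so some stays will be shorter.

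**Working it through.** **Plan's own figure.** Inputs from Sections 10.2 and 10.3: 65% v 35%, two-sided 0.05, power 90%. n = [1.960 × √(2 × 0.5 × 0.5) + 1.2816 × √(0.65 × 0.35 + 0.35 × 0.65)]² / 0.30² = 56.3, so 57 per group. With continuity correction, (56.3/4) × [1 + √(1 + 4/(56.3 × 0.30))]² = 62.8, so 63. Then 63/0.9 = 70 per group, 140 in total. The sample size reproduces and is not in dispute. Exact power of the uncorrected χ² test at 63 per group is 93.7%.

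**Gap between two hourly scores.** If both neighbours are 3 or less, their mean is 3 or less: 0 of the 4 × 4 = 16 integer pairs exceed 3. If either neighbour is above 3, the patient is already an event. The fill therefore never changes a classification.

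**Hour 1 missing.** The first scheduled postoperative score is hour 1, so there is no earlier score to average.

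**Hour 4 missing.** With hour 3 at 3, 2, 1 or 0, a later score of at least 4, 5, 6 or 7 gives a mean above 3. That is 7 + 6 + 5 + 4 = 22 of 44 possible pairs. This counts pairs, not patients. For the timing, suppose surgery ends at noon. The window closes at 4pm, and the 10pm self-rating covers 2pm to 10pm: two hours inside the window and six after it.

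**Size, under an assumed model.** The documents give neither a missingness rate nor a correlation between scores. The assumptions are exchangeable hourly scores rounded to 0–10, correlation 0.5 to 0.8, SD 1.5 to 2.5, and a mean set so that 65% or 35% of patients have an event; 400,000 simulated patients per setting.

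| Missing score and fill | 65% event rate | 35% event rate |
|---|---|---|
| Hour 2 or 3: events lost, % of patients with that gap | 3.3 to 6.0 | 3.0 to 5.0 |
| Hour 4, later eight-hour maximum, pain does not fall: net shift in points | +3.1 to +6.1 | +2.7 to +4.9 |
| Hour 4, single later reading, pain does not fall: net shift in points | −3.3 to −1.0 | −3.2 to −1.1 |

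Section 10.1 points towards a fall in pain: an average score above 3 in 65% over the first four hours (its count of 35 of 50 is 70%) and in 35% after eight hours. A fall of 1 to 1.5 points phased in over hours 5 to 8 changes the hour-4 net shift with the eight-hour maximum to about −2.4 to +0.8 points across both event rates. A fall matched to 65% v 35% (about 0.9 to 1.8 points) gives −1.6 to +0.5 if gradual and −2.6 to −1.0 if immediate. Section 10.1 reports averages, so this calibration is approximate.

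**Effect on the comparison.** Assume 20% of patients miss hour 4, filled from the maximum, with no fall in pain.

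- Both arms: each rate rises by 0.2 × (2.7 to 6.1) = 0.5 to 1.2 points, and the difference moves by less than 0.3.
- One arm only: the difference moves by 0.5 to 1.2 points.

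For scattered, balanced gaps:

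- 5% of readings missing: 63 × (1 − 0.95⁴) = 11.7 patients per arm have a gap, and 0.4 to 0.9 are misclassified.
- 10% missing: 63 × (1 − 0.90⁴) = 21.7 have a gap, and 0.8 to 1.8 are misclassified.
- Power stays between 93.0% and 93.7%.

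**The case against.** The strongest reply is that little turns on this. Scattered gaps misclassify fewer than two patients per arm, power barely moves, and balanced hour-4 gaps almost cancel in the difference. Patients, treating staff and investigators are blinded. That stands, and it limits the weight of the point.

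Second, the hour-4 route is one reading. Section 10.8 does not say that a ward maximum may stand in for an hourly score. If neighbours must be hourly scores, hour 4 is simply undefined, like hour 1. That is fair, but the text does not restrict the neighbours, and either reading leaves hour 4 without a sound rule.

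Third, the difference between Sections 9.2 and 9.4 may be partly language, since the word joining the two clauses is used loosely throughout. A reader might infer that early transfer leaves hourly scores missing by design. The documents do not establish that: Section 9.2 expressly includes the ward. The wording still has to be reconciled, because ward staff who followed 9.4 would produce the gaps.

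Fourth, a reader might take 22 of 44 as a 50% risk of a false event, or take the upward hour-4 shift as settled. Neither holds. The pairs are not equally likely, and the sign depends on whether pain falls after hour 4.

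**Conclusion.** The concern holds and should be fixed. The neighbour mean is a stated rule for the primary endpoint that cannot add an event in a mid-series gap, has no value at hour 1, and at hour 4 may draw on pain from outside the window. Those three statements follow from the text and arithmetic alone.

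The sizes rest on the assumed model. A single mid-series gap costs about 3 to 6 events per 100 patients with that gap. For hour 4 filled from a ward maximum, the net shift is about +3 to +6 points if pain does not fall and about −2.4 to +0.8 points if it falls gradually by 1 to 1.5 points. An immediate fall pushes it lower. The direction is therefore uncertain.

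A reader might infer that the rule biases the comparison towards one arm. The documents do not support this. They give no missingness rate, and nothing in them suggests that gaps or early transfers differ by arm. With few, balanced gaps the effect on the difference and on power is small; it grows if gaps are common or uneven.

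**What to change.** 1. Reconcile Section 9.4, Section 5.2 and the study sequence table with Section 9.2, so that hours 1 to 4 are scored wherever the patient is.
2. For the primary endpoint, drop the neighbour mean. Any observed hourly score above 3 is an event; four observed scores of 3 or less are a non-event; any other pattern is undetermined.
3. Name the primary handling of undetermined patients. Options are multiple imputation of the missing hourly scores from the observed hourly scores and arm, or explicitly counting missing as an event in both arms.
4. Add two sensitivity analyses, all undetermined patients as non-events and all as events, which bound each arm's event rate.
5. Do not average a ward eight-hour maximum, or any score after hour 4, into an hourly score. A ward maximum of 3 or less whose period covers the missing hour may be used to confirm a non-event at that hour.
6. Report missing scores by hour and arm.

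Section 10.7 already sends statistical deviations through a protocol amendment, so the change belongs there, before analysis. The cost is wording, a few ward scores that Section 9.2 already requires, and a little more analysis. Event rates may move slightly either way.

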Postoperative pain is a common problem in today`s surgery, although pain management techniques have improved in the last years. Systemic application of lidocaine has gained interest since several studies have shown its analgesic, anti-inflammatory and anti-hyperalgesic properties. This study will be conducted to evaluate the analgesic efficacy of systemic lidocaine in addition to total intravenous anesthesia in morbidly obese patients undergoing laparoscopic bariatric surgery.

Objective

To investigate if intravenous administration of lidocaine in patients undergoing bariatric surgery reduces postoperative pain intensity within the first four hours after completion of surgery.

Hypothesis

Perioperative treatment of patients undergoing bariatric surgery with lidocaine reduces the proportion of those suffering from more intensive pain (any development of VAS/NRS score > 3, in hourly measurements) within the first four hours from currently 65% to 35%.

Outcome

Primary: proportion of patients suffering from higher pain intensity (any development of VAS/NRS score > 3, in hourly measurements) within the first four hours after completion of bariatric surgery.

Secondary: average maximal pain intensity during first four hours and during 48 hours, total opiate consumption, postoperative nausea and vomiting, time to first defecation and length of hospitalization.

Study design

Prospective, randomized, double blinded, placebo controlled trial

Inclusion / Exclusion criteria

Inclusion: elective laparoscopic bariatric surgery, ASA classification I – III, age 18 – 80, informed consent

Exclusion: no written consent, allergy to the investigational product, cardiac arrhythmia (pacemaker), liver dysfunction (Child-Pugh classification A, B or C), pregnancy, central nervous disease, chronic pain and pre-existing opiate prescription, expected non-compliance, drug/alcohol abuse

Study Product / Intervention

“lidocaine group”

- *1.5 mg/kg lean body mass lidocaine (lidocaine 1%) bolus I.V. as general anesthesia steady state concentration is accomplished*
- *1.5 mg/kg lean body mass/h lidocaine I.V. with beginning of surgical procedures*
- *after completion of surgery: transfer to PACU, pain evaluation (VAS/NRS score questionnaire, see appendix for detailed questionnaire) for 48 hours, nurse –based pain treatment as appropriate*
- *duration of intervention: lidocaine infusion up to four hours from completion of surgery, or till transfer to surgical ward*

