
glycinexylidide (MEGX) and then subsequently to the inactive glycine xylidide. MEGX has a longer half-life than lidocaine, but also is a less potent sodium channel blocker. (47 - 49) Lidocaine elimination in patients with liver cirrhosis was examined by Wojcicki et al.. Their findings indicated higher plasma concentrations of lidocaine and lower concentration of MEGX, dependent on the stage of liver dysfunction (Child-Pugh A to C). (57) Current studies, setting the focus on abdominal surgery, indicated that the systemic application of lidocaine was associated with fewer intensity of pain at rest and during mobilization and resulted in a decrease of patients' opiate consumption. Studies evaluating patients receiving orthopedic and neurosurgical interventions did not show any benefit from lidocaine I.V. (28 - 30). This discrepancy is most likely explained by the different development of inflammation due to visceral and somatic pain induction. Noteworthy is the fact, that local anesthetics can suppress the overreacting immune-signaling due to surgical intervention, without interfering with the physiological immune-signaling. Studies showed an inhibition of white blood cells' priming (as a principle for immune-reaction, the prearrangement of granulocytes to a following inducing signal leads to a up to 20-times exaggerated release of superoxides) due to the implementation of systemic lidocaine. Interestingly, lidocaine impedes the priming, which represents a common reaction to tissue damage induced by surgery, without inhibiting the classic activation of neutrophil granulocytes. (31) A major reason for patients' discomfort, prolonged recovery, length of hospital stay and thereby resulting, higher morbidity and increased financial costs, are post-surgical complications, especially gastrointestinal dysfunction and postoperative nausea and vomiting (PONV) due to surgical inflammation and increased opiate consumption. Average incidence of PONV after abdominal surgery in general anesthesia ranges between 25 – 30%. Pathogenic mechanisms are complex but are traced back to the neural and inflammatory response and stimulation after surgical interventions. A study by Groudine et al. showed that patients receiving systemic lidocaine during radical prostatectomy regained gastrointestinal motility faster and required less opiates after the intervention compared to an application of placebo during surgery. (32, 33) However, lidocaine seems to be profitable to patients undergoing abdominal surgery as meta analyses demonstrate. Inhibition of myenteric plexus reflex as a target might play a role in the effectiveness of systemically administered lidocaine, as well as a reduction of interleukin-6 (IL-6) which could be significantly reduced in a study examining patients receiving systemic lidocaine during colorectal surgery (32, 34).

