5.3 Other outcomes of interest

- any event of postoperative nausea and vomiting (subdivided by event of no nausea (PONV = 0), event of nausea without vomiting (PONV = 1) and event of nausea with vomiting (PONV = 2)) during first 48 hours after completion of surgery
- time to first defecation (quantified in hours)
- duration of hospitalization (quantified in days)

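### Scoring missing PONV data as no PONV lowers the event rate and can create a false difference between arms when missingness differs

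*Combined protocol and SAP*

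**What the plan says.** Section 10.8 gives an explicit rule: missing PONV data "will be handled as no occurrence of PONV (PONV 0". Section 5.3 defines the outcome as "any event of postoperative nausea and vomiting" and grades it as "event of no nausea (PONV = 0), event of nausea without vomiting (PONV = 1) and event of nausea with vomiting (PONV = 2", with a window of "during first 48 hours after completion of surgery". PONV 0 is therefore an assessed state, and the most favourable one.

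Section 10.8 also removes drop-outs from the analysis altogether, so the PONV rule acts only on patients who stay in. Section 10.5 tests dichotomous outcomes by chi-square at p < 0.05. The plan has no observed-data analysis or sensitivity analysis for PONV, does not ask for missing counts by arm, and states no expected amount of missing PONV data.

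The status of the endpoint varies. The synopsis lists among the secondary outcomes "total opiate consumption, postoperative nausea and vomiting, time to first defecation and length of hospitalization", and sections 9.2 and 10.8 also call PONV secondary, while sections 4.3 and 5.3 place it among the other objectives and outcomes of interest.

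**The concern.** A blank is not a recorded zero. For a patient with no usable PONV record over 48 hours, the rule can turn an event into a non-event but never the reverse, so it can only lower the PONV rate. If the two arms have different shares of such patients, the rule produces a difference that has nothing to do with lidocaine. If the shares are equal, the risk ratio survives but the absolute difference shrinks.

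Little else in the plan would limit this. Section 9.4 sets out when pain is scored but gives no schedule for PONV. Section 5.4 says PONV is not counted as an adverse event (although it lists nausea and vomiting among possible adverse events), so adverse event reporting need not recover a missing score. What is at stake is one secondary or other comparison that will be tested and published, not the primary result.

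**Working it through.** **The plan's own figure.** No figure is stated for PONV. The only computable design figure is the primary sample size, used here only to set the number per arm. For 65% v 35%, two-sided alpha 0.05 and 90% power (section 10.3):

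- n = [1.960 × √(2 × 0.5 × 0.5) + 1.2816 × √(0.65 × 0.35 + 0.35 × 0.65)]² / 0.30² = 56.3, that is 57 per arm without continuity correction.
- With continuity correction, n = (56.3/4) × [1 + √(1 + 4/(56.3 × 0.30))]² = 62.8, that is 63, as stated.
- 126/0.90 = 140, as stated. So 63 per arm is the number expected after drop-outs are removed.

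**Inputs for PONV.** Section 3.1 reads "Average incidence of PONV after abdominal surgery in general anesthesia ranges between 25 – 30" percent. This is a background figure for abdominal surgery in general, used here as an illustrative true rate p. The shares missing (m) are assumptions, from 0 to 20% of retained patients per arm. Below, C is placebo, L is lidocaine, and differences are lidocaine minus placebo.

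**Step 1: one arm.** If missingness is unrelated to PONV, the analysed rate is p(1-m).

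- 10% missing: 0.25 × 0.90 = 22.5%; 0.30 × 0.90 = 27%.
- p = 30% with 5% or 20% missing: 28.5% or 24%.

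**Step 2: no true effect, unequal missingness.** The false difference is p(m_C - m_L). Rejection probabilities are for a two-sided pooled-variance test at 63 per arm.

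| p | Missing, C v L | Analysed, C v L | Difference (points) | Risk ratio | Rejection |
|---|---|---|---|---|---|
| 30% | 5% v 10% | 28.5% v 27.0% | -1.5 | 0.95 | 5.4% |
| 30% | 5% v 15% | 28.5% v 25.5% | -3.0 | 0.89 | 6.7% |
| 30% | 15% v 5% | 25.5% v 28.5% | +3.0 | 1.12 | 6.7% |
| 30% | 0% v 20% | 30.0% v 24.0% | -6.0 | 0.80 | 11.8% |
| 25% | 5% v 15% | 23.75% v 21.25% | -2.5 | 0.89 | 6.3% |
| 25% | 0% v 20% | 25.0% v 20.0% | -5.0 | 0.80 | 10.3% |

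Check of the second row: the pooled rate is 0.27, so the null standard error is √(2 × 0.27 × 0.73/63) = 0.079 and the critical difference is 1.96 × 0.079 = 0.155. With a shift of 0.03, the two tails are about 5.7% and 1.0%, together about 6.7%.

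**Step 3: a true effect (assumed 30% v 15%).**

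- 10% missing in both arms: 27% v 13.5%. The risk ratio stays at 0.50, the difference falls from 15 to 13.5 points, and power falls from 52% to 47%.
- 5% v 15% missing: risk ratio 0.1275/0.285 = 0.45. With 15% v 5%: 0.1425/0.255 = 0.56. The truth is 0.50.
- In general the risk ratio is multiplied by (1-m_L)/(1-m_C), so it always moves in favour of the arm with more missing data. The risk difference moves by p_C·m_C - p_L·m_L. It follows the same direction when the true rates are equal, but need not when they differ.

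**Step 4: missingness related to PONV.** Suppose the true rate is 30%, 10% of patients are missing, and 60% of those had PONV (both shares assumed). The rule gives 0.30 - 0.10 × 0.60 = 24%. Analysing observed patients only gives 0.24/0.90 = 26.7%. That is closer to 30% but still low.

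**Step 5: bounds.** With 30% observed among assessed patients, counting the missing as all without or all with PONV gives 28.5% to 33.5% at 5% missing, 27% to 37% at 10%, and 24% to 44% at 20%.

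**The case against.** The best defence is that the rule will seldom matter. The outcome is any event over 48 hours, and patients are seen repeatedly in the recovery unit and on the ward, so a single missed contact does no harm when another contact records PONV. Drop-outs are excluded. The trial is double-blind with identical syringes, and the rule is prespecified and applied alike in both arms. A false 3-point difference is about 2 patients in 63 (0.03 × 63 = 1.9), under 0.4 of its standard error of about 7.9 points. Most of this stands, and it limits the size of the problem. It does not justify the rule, which acts only when data are missing and then always in the favourable direction.

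Several stronger readings are tempting, and the documents do not support them:

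- A reader might infer that imputed zeros make the standard error too small. They do not. Under the rule each patient's score is a 0/1 variable with probability p(1-m), and the usual binomial standard error is right for that quantity. With equal missingness and no true effect, rejection stays at 5%. The fault is bias.
- A reader might infer that missing patients are the sedated or sicker ones. The documents do not say so, and p(1-m) does not need it.
- A reader might infer that the rule favours lidocaine. With equal true rates it favours whichever arm has more missing data, and nothing in the plan shows which that would be.
- A reader might take 25-30% as this trial's expected PONV rate. Section 10.1 says PONV was reviewed in local bariatric records but gives no rate.

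**Conclusion.** The concern holds for retained patients who have no usable PONV record. For them the rule lowers the PONV rate, and the comparison is distorted when the arms differ in missingness. With differences in missingness of 10 points or less, the false difference is at most about 3 points and the rejection probability about 6 to 7%. With 0% v 20% missing, these become 5 to 6 points and 10 to 12%. These sizes rest on assumed missingness, on the background rate of 25-30%, and, for the arm comparison, on missingness unrelated to PONV within each arm. The primary endpoint and the 63 per group are untouched. The rule should be changed because the change is cheap and nothing else in the plan corrects it.

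**What to change.** In section 10.8, delete the PONV 0 imputation and put in its place:

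- Score any PONV over 48 hours from all available assessments. State in advance what counts as a usable assessment, and how a patient with some assessments missing and no recorded event is scored.
- Treat patients with no usable assessment as missing. Analyse observed data, or use multiple imputation.
- Report the number missing in each arm.
- Add best-case and worst-case sensitivity analyses. They are needed because, as step 4 shows, observed-data analysis does not fully remove the bias if missingness depends on PONV.

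The cost is a wording change, made by the amendment that section 10.7 requires and preferably before unblinding, plus the sensitivity analyses. The downside is a slightly smaller evaluable number: with 10% missing, about 57 instead of 63 per arm (63 × 0.90 = 56.7).
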